This will be an exploratory, single site randomized controlled trial with 60 patients equally allocated to the PAS intervention or an ATT control group (see Schema section above). Based on the ORBIT framework (which has application beyond the topic area of obesity), this study is a Phase II Preliminary Testing trial. Randomization will be stratified according to gender and presence of self-reported pain (≥3 on a 10 point scale) in any lower extremity joint (hip, knee or ankle) in addition to the surgical knee, to ensure that the groups are balanced in these respects. We chose patient-level randomization because it is a straight-forward design that avoids potential biases and challenges of cluster randomization, such as imbalances in participant characteristics across study arms and attrition of study physical therapists 41,42. With this design, each study therapist can treat patients in both study arms. Although the PAS program will involve discrete components that are distinct from usual post-TKA PT (which will be delivered to the ATT control group), we acknowledge the risk of contamination of intervention delivery. To mitigate this risk, we will employ an intensive fidelity monitoring process, described below and in the Intervention Documents. If we find in this exploratory study that contamination is a concern, clinic-level randomization will be considered for a larger trial. The typical length of post-TKA PT is about 12 weeks. We will enroll patients approximately 4 weeks from initiation of outpatient PT, allowing time for randomization and notification of the treating therapist to begin the PAS intervention before PT is complete. Follow-up assessments will be conducted 3 months after the beginning intervention visits (shortly following to the end of the PAS intervention) and after 6 months (sustainability end point). Regarding the 3-month follow-up time point, we selected this interval because it will: 1) allow for several weeks for participants to act on content delivered in the 8-week intervention visit and 2) allow sufficient time for scheduling first follow-up assessments after all intervention visits have been complete. Longer term outcomes will be included in a larger trial.

Version 11.0 6 October 2022

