9.2 SAMPLE SIZE DETERMINATION

No adjustment for co-primary outcomes is made since this is a pilot study. We do not necessarily expect this exploratory study to be highly powered. Table 3 shows a range of effect sizes and corresponding statistical power for a comparison of intervention versus control group means, for the projected total of n=54 participants at the two-sided 0.05 significance level. We chose n=54 because this is reasonable to complete within the time frame of this exploratory trial and will allow sufficient experience to inform a larger trial. We are allowing for a 10% attrition rate, so n=60 participants will be enrolled. Data from this study are crucial for informing sample size estimates for a larger trial; however, preliminary calculations indicate that for a standardized effect size of 0.35-0.40 standard deviation units, a sample size of 100-130 per group may be required. This sample size is reasonable to enroll within the time frame of this exploratory trial, and it will allow sufficient experience with intervention delivery to inform the larger trial. Our analytic strategy (described below) will also accommodate dropout, missed visits, and loss-to-follow-up. Information regarding the actual observed extent of dropout, missed visits, and loss-to-follow-up in this study will also be useful for the subsequent large-scale trial.

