9.4 STATISTICAL ANALYSES PLAN

Preliminary analyses will include generating descriptive statistics for demographic variables, as well as baseline characteristics and follow-up measures. This includes means and standard deviations for continuous variables, and frequencies and percentages for categorical variables. Ranges will also be examined for outliers and to ensure data integrity. Demographics and baseline characteristics will also be described separately by randomized group. Statistical tests will be performed to compare each of these by randomized group to determine the extent of random imbalance by t-test of chi-square testing, as appropriate. However, the p-values generated by these tests are considered as descriptive rather than as inferential. We would

expect some imbalance between the groups by random chance, owing to the limited sample size. Variables exhibiting imbalance may be considered as covariates in the statistical models described below.

The co-primary outcome of MVPA will be analyzed across the follow-up time points through a general linear mixed model (GLMM). Specifically, the MVPA values at 8 weeks and at 6 months for a given patient will form their response vector for this model. Fixed effects for the primary model will include an indicator for PAS group, an indicator for the 6-month follow-up time point, their interaction (group by time), and baseline MVPA value; a supporting model will also include any covariates that exhibit random imbalance between groups at baseline. Random effects for patients will account for the within-patient correlation induced by the repeated measures design. Formal statistical testing of the group by time interaction term will provide assessment for whether efficacy varies by follow-up time point. A term representing the interaction of PAS-by-baseline value will be included and tested to explore whether participants' starting point might impact how much they improve; it will be removed if non-significant attention. Statistical contrasts will be constructed in order to estimate the effect of PAS versus attention control, separately at 8 weeks and at 6 months; these estimates will inform the sample size estimation of the subsequent trial. Estimated correlations among follow-up time points will also be useful in this regard.

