The approach outlined above will be repeated for the co-primary outcome of peak joint loading symmetry during gait, through fitting a separate GLMM. The main difference will be to include walking speed as an additional covariate, as justified in the research strategy. Secondary outcomes will also be analyzed using the same approach, each with its own GLMM.

An exploratory analysis will include KOOS pain scores as a (time-dependent) main effect, as well as their interaction with PAS, to evaluate whether this variable has an impact on intervention effects. This exploratory analysis will be repeated, but using participant-specific changes in KOOS pain scores, to examine how our primary outcomes (MVPA and peak load symmetry during walking) are associated with those changes.

If any of the co-primary or secondary outcomes exhibit distributions that deviate markedly from normality, alternatives will be considered. First, transformations, such as the natural logarithm, will be applied in an attempt to normalize the distribution. If this is not successful in remedying the non-normality, alternatives such as categorizing the variable and applying appropriate categorical data analysis, such as logistic mixed models (with a similar specification as described above for the GLMMs) or logistic models utilizing generalized estimating equations methodology can be fitted.

A two-sided 0.05 significance level will be applied to each co-primary outcome, as well as each secondary outcome; no adjustment for multiple comparisons will be applied. This is consistent with the trial's objective as a pilot study to generate estimates useful for the large-scale trial to follow.

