MVPA and peak joint loading symmetry during gait will be treated as co-primary outcomes. However, no adjustment for multiplicity is made due to the pilot nature of this study, with an objective of generating estimates suitable for the power analysis for the subsequent large-scale trial. Also owing to the pilot nature of this exploratory trial, we do not necessarily expect to have a highly powered study; rather, the large-scale trial that follows will aim to accomplish this objective. In the Table below we demonstrate a range of effect sizes (in standard deviation units) and the corresponding statistical power that would apply for a comparison of

intervention versus control group means at the two-sided 0.05 significance level, for the projected total of n=54 participants (n=27 per group) with complete data. Due to expected attrition of 10%, we will enroll n=60 participants into the trial. This sample size is reasonable to enroll within the time frame of this exploratory trial, and it will allow sufficient experience with intervention delivery to infer

Statistical power according to effect size,					
assuming 27 patients per group					
Effect Size (SD units)					
0.5	0.6	0.7	0.8	0.9	1.0
0 44	0.58	0.71	0.82	0.90	0.95

and it will allow sufficient experience with intervention delivery to inform the larger trial. Our analytic strategy (described below) will also accommodate dropout, missed visits, and loss-to-follow-up. Information regarding the actual observed extent of dropout, missed visits, and loss-to-follow-up in this study will also be useful for the subsequent large-scale trial.

Analytic Techniques and Handling of Missing Data

Preliminary analyses will include generating descriptive statistics for demographic variables, as well as baseline characteristics and follow-up measures. This includes means and standard deviations for continuous variables, and frequencies and percentages for categorical variables. Ranges will also be examined for outliers and to ensure data integrity. Demographics and baseline characteristics will also be described separately by randomized group. Statistical tests will be performed to compare each of these by randomized group to determine the extent of random imbalance by t-test of chi-square testing, as appropriate. However, the p-values generated by these tests are considered as descriptive rather than as inferential. We would

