expect some imbalance between the groups by random chance, owing to the limited sample size. Variables exhibiting imbalance may be considered as covariates in the statistical models described below.

The co-primary outcome of MVPA will be analyzed across the follow-up time points through a general linear mixed model (GLMM). Specifically, the MVPA values at 8 weeks and at 6 months for a given patient will form their response vector for this model. Fixed effects for the primary model will include an indicator for PAS group, an indicator for the 6-month follow-up time point, their interaction (group by time), and baseline MVPA value; a supporting model will also include any covariates that exhibit random imbalance between groups at baseline. Random effects for patients will account for the within-patient correlation induced by the repeated measures design. Formal statistical testing of the group by time interaction term will provide assessment for whether efficacy varies by follow-up time point. A term representing the interaction of PAS-by-baseline value will be included and tested to explore whether participants' starting point might impact how much they improve; it will be removed if non-significant attention. Statistical contrasts will be constructed in order to estimate the effect of PAS versus attention control, separately at 8 weeks and at 6 months; these estimates will inform the sample size estimation of the subsequent trial. Estimated correlations among follow-up time points will also be useful in this regard.

The approach outlined above will be repeated for the co-primary outcome of peak joint loading symmetry during gait, through fitting a separate GLMM. The main difference will be to include walking speed as an additional covariate, as justified in the research strategy. Secondary outcomes will also be analyzed using the same approach, each with its own GLMM.

An exploratory analysis will include Knee injury and Osteoarthritis Outcome Score (KOOS) pain scores as a (time-dependent) main effect, as well as their interaction with PAS, to evaluate whether this variable has an impact on intervention effects. This exploratory analysis will be repeated, but using participant-specific changes in KOOS pain scores, to examine how our primary outcomes (MVPA and peak load symmetry during walking) are associated with those changes.

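### The co-primary mixed models carry baseline as a main effect only, so the group-by-time estimate is not baseline-adjusted and both visit contrasts share one averaged slope; a baseline-by-time term is a cheap gain in precision

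*Protocol*

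**What the plan says.** Protocol 9.4 puts the two follow-up MVPA values in the response vector and lists the fixed effects as a PAS indicator, "an indicator for the 6-month follow-up time point, their interaction (group by time), and baseline MVPA value". The SAP, under Analytic Techniques and Handling of Missing Data, has the same list: "Fixed effects for the primary model will include an indicator for PAS group, an indicator for the 6-month follow-up time point", followed by the interaction and the baseline value. Patient random effects carry the within-patient correlation.

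For load symmetry, Protocol 9.4 states: "The approach outlined above will be repeated for the co-primary outcome of peak joint loading symmetry during gait, through fitting a separate GLMM", with walking speed added. Secondary outcomes follow the same approach, each in its own model.

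Two other provisions involve baseline:

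- A PAS-by-baseline term is tested and removed if non-significant.
- A supporting model adds covariates that turn out imbalanced.

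Neither lets the effect of baseline differ between visits. From this model the plan takes a formal group-by-time test and separate PAS contrasts at the two follow-ups, which are to help size the next trial. The plan says it expects some chance imbalance at this sample size.

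The model text calls the first follow-up 8 weeks, while the Protocol's hypotheses and schedule call it 3 months. That is a separate inconsistency; I write 3 months throughout.

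**The concern.** The model is asked visit-specific questions but has only one baseline slope. Baseline is measured during recovery. Protocol 4.1 says "We will enroll patients approximately 4 weeks from initiation of outpatient PT", in a course that typically lasts about 12 weeks. A measurement taken then may well predict the earlier follow-up better than the later one. If so, the averaged slope adjusts too little at 3 months and too much at 6 months. Any chance baseline difference between arms then pushes the two contrasts in opposite directions.

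A reader would also expect the group-by-time test to be baseline-adjusted, since baseline is in the model, but in the planned form it is not. At stake are the precision of that test and the accuracy, given the imbalance that actually occurs, of the visit-specific estimates carried into the next trial.

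**Working it through.** **Inputs from the documents.** Protocol 9.2 plans power "for the projected total of n=54 participants at the two-sided 0.05 significance level"; the SAP table is headed "assuming 27 patients per group". The test level is two-sided 0.05 without multiplicity adjustment ("A two-sided 0.05 significance level will be applied to each co-primary outcome, as well as each secondary outcome"). The documents give no figure for baseline slopes, so there is no stated result on this point to reproduce. The sample size does reproduce: 54/(1 - 0.10) = 60, as in "We are allowing for a 10% attrition rate, so n=60 participants will be enrolled". Noncentral-t power at 27 per group is 0.438, 0.581, 0.714, 0.822, 0.901 and 0.950 for effects of 0.5 to 1.0 SD, matching every entry in the SAP table.

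**Assumptions of mine.** Unit SDs, residual correlation 0.5, complete data, a single random intercept, and slopes b3 and b6 of the 3- and 6-month outcomes on baseline.

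**Step 1: what the planned model estimates.** With two complete visits, the random-intercept fit splits into a regression of the visit mean on group and baseline, and a regression of the within-patient change on group. A baseline main effect is constant over time, so it drops out of the change. A PAS-by-baseline term drops out for the same reason. A fitted mixed model on one simulated data set confirms this:

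- planned group-by-time estimate: -0.04621
- raw difference in change: -0.04621
- with baseline-by-time added: -0.06348, equal to the baseline-adjusted difference in change

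**Step 2: conditional error.** Let D be the PAS-minus-control difference in mean baseline. The averaged slope is (b3 + b6)/2, so the error is +(b3 - b6)/2 × D at 3 months, -(b3 - b6)/2 × D at 6 months, and -(b3 - b6) × D for group-by-time (6 minus 3 months).

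- SD of D at 27 per arm: sqrt(2/27) = 0.272.
- Median |D|: 0.6745 × 0.272 = 0.18.
- P(|D| > 0.4): 0.4/0.272 = 1.47, giving about 0.14 (0.12 with 30 per arm).
- Slopes 0.7/0.4 at |D| = 0.18: 0.15 × 0.18 = about 0.03 SD per visit and 0.3 × 0.1836 = 0.055 SD for group-by-time.
- Slopes 0.7/0.4 at |D| = 0.4: 0.06 and 0.12 SD.

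**Step 3: variance.** Let s3² = 1 - b3², s6² = 1 - b6², c = 0.5 × s3 × s6, sd² = s3² + s6² - 2c (change), sm² = (s3² + s6² + 2c)/4 (visit mean) and Δ = b3 - b6. In units of 2/27, with N = 54:

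- planned visit contrast: s² + Δ²/4 + sm²/(N - 4), where s² is s3² or s6²
- visit contrast with the term: s² × (1 + 1/(N - 4)) = 1.02 s²
- planned group-by-time: sd² + Δ²
- group-by-time with the term: 1.02 sd²

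For 0.7/0.4: s3² = 0.51, s6² = 0.84, c = 0.3273, sd² = 0.6955, sm² = 0.5011, Δ² = 0.09.

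- 3 months: (0.51 + 0.0225 + 0.0100)/0.5202 = 1.043
- 6 months: (0.84 + 0.0225 + 0.0100)/0.8568 = 1.018
- group-by-time: 0.7855/0.7094 = 1.107

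Variance ratio, planned over with-term:

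| Slopes (3, 6 months) | 3 months | 6 months | Group-by-time |
|---|---|---|---|
| 0.55 / 0.55 | 0.995 | 0.995 | 0.980 |
| 0.70 / 0.55 | 1.009 | 1.001 | 1.017 |
| 0.65 / 0.45 | 1.015 | 1.005 | 1.037 |
| 0.70 / 0.40 | 1.043 | 1.018 | 1.107 |

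Planned standard errors for 0.7/0.4 are sqrt(0.5425 × 2/27) = 0.20, sqrt(0.8725 × 2/27) = 0.25 and sqrt(0.7855 × 2/27) = 0.24 SD. Simulation agrees with these ratios.

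**Step 4: error rates.** With slopes 0.7/0.4 and no true effect, the simulated group-by-time rejection rate averaged over randomisations is 0.054 with or without the added term. Given an imbalance of 1.96 standard errors (0.533 SD), it is 0.083 as planned and 0.050 with the term.

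**The case against.** The strongest reply is that the planned analysis is valid. A raw between-arm difference in change is a legitimate estimator, and randomisation keeps it and both visit contrasts unbiased. This stands. A reader might infer from opposite shifts at the two visits that the plan yields biased or spurious effects. The documents do not support that: the shifts depend on the realised imbalance and average to zero.

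Second, unequal slopes are an inference. No section gives a slope or correlation. On the Protocol's schedule both follow-ups count from the next-to-last PT visit. If that visit falls near week 11-12 of PT (my assumption), the gaps from baseline are about 20 and 34 weeks, a ratio of 1.7. Pure exponential decay then takes 0.70 to 0.70^1.7 = 0.55, which is the mild row of the table. The SAP's timing (enrolment at about 8 weeks, first follow-up 8 weeks after randomisation) makes the ratio larger, so the two documents leave the matter open. This part stands: steep slope differences should not be presented as expected.

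Third, a 0.4 SD imbalance is not typical, since it arises in about 14% of trials. The typical shift of 0.03 SD is small beside a standard error of 0.20-0.26 SD. This also stands.

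What remains is that the model omits a conventional term needed to adjust the group-by-time estimate for baseline, and no other provision in the plan supplies it.

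**Conclusion.** The point holds as a modest improvement in precision and conditional accuracy, not as the correction of a biased analysis. What is certain, given complete data and a random intercept, is structural: the group-by-time estimate is unadjusted for baseline and the two contrasts share one slope.

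The size rests on assumed slopes. The gain is negligible for the visit contrasts when the slopes are close and reaches about 4% of variance at 0.7/0.4. For group-by-time it runs from about 2% to about 11%. Against the standardised effect of 0.35-0.40 SD used in Protocol 9.2 for the larger trial, a 0.03 SD shift is minor; the 0.06 SD shift in a less balanced trial is 15-17% (0.06/0.40 to 0.06/0.35).

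The calculation does not cover missing visits or the walking-speed covariate in the load-symmetry model, so the exact cancellation in Step 1 is not claimed there. Nor does it bear on the random intercept's assumption of equal variance at both visits, which this change leaves in place.

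**What to change.** In Protocol 9.4 and the SAP, add a baseline-by-time interaction to the fixed effects of both co-primary models and of the secondary models that use the same approach. State that it is kept whatever its significance, unlike the PAS-by-baseline term. Take the visit-specific PAS contrasts (evaluated at a common baseline value) and the group-by-time test from that model.

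The cost is a wording change and one parameter per model. If the two slopes are equal, variance rises by about 0.5% for the visit contrasts and 2% for group-by-time. Data collection and trial conduct are unaffected.

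### Read as a random intercept, the patient random effect ties both follow-ups to one variance, so the separate per-visit standard errors err in opposite directions if the spread differs between visits

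*Protocol*

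**What the plan says.** Section 9.4 of the Protocol and the SAP section on analytic techniques and missing data carry the same text. On the response: "Specifically, the MVPA values at 8 weeks and at 6 months for a given patient will form their response vector for this model". Baseline enters as a covariate. The fixed effects are group, time, group by time, and the baseline value. On dependence within a patient, the only statement is "Random effects for patients will account for the within-patient correlation induced by the repeated measures design".

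Contrasts of PAS against attention control are then formed at each follow-up separately, and "these estimates will inform the sample size estimation of the subsequent trial". The same model is to be fitted to load symmetry (adding walking speed) and to every secondary outcome, each tested at a two-sided 0.05.

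Neither document names a residual covariance structure, visit-specific variances, a robust variance or a degrees-of-freedom method. The one fallback, transforming and then categorising, is triggered by marked non-normality and not by unequal variance.

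I write first follow-up throughout because section 9.4 and the SAP place it at 8 weeks, while Protocol sections 1.3 and 9.1 place it at 3 months. Those passages must be reconciled, but the label does not affect this point.

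**The concern.** With two visits, a patient intercept plus a single residual variance is compound symmetry: one variance for both visits and a non-negative correlation. A contrast at a single visit takes its standard error from that common variance. If outcomes are more variable at one visit than at the other, the standard error is too small where the spread is larger and too large where it is smaller. Having only two time points does not protect a contrast made at one of them.

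Unequal spread is possible here. Protocol section 4.1 places the first follow-up shortly after the intervention ends and treats 6 months as a test of sustainability. Nothing in the documents supports or refutes equal variance.

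At stake are the confidence intervals and p-values for the per-visit effects, which are the main quantitative output of this pilot.

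**Working it through.** **Inputs.** Two-sided 0.05 and 54 analysed (Protocol 9.2: "for the projected total of n=54 participants at the two-sided 0.05 significance level"). 27 per group (SAP: "for the projected total of n=54 participants (n=27 per group) with complete data"). Sixty enrolled (Protocol 9.2: "We are allowing for a 10% attrition rate, so n=60 participants will be enrolled"). Equal allocation (Protocol 4.1: "60 patients equally allocated to the PAS intervention or an ATT control group"). No SD is given for either follow-up, so the SD ratio and the within-patient correlation below are assumptions.

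**The plan's own figures.** Two-sample t-test power with 27 per group (52 df, noncentrality d × √(27/2)) at d = 0.5, 0.6, 0.7, 0.8, 0.9, 1.0 is 0.438, 0.581, 0.714, 0.822, 0.901, 0.950. This matches all six SAP values. Enrolment follows from 54/(1 − 0.10) = 60. The table is a simple comparison of two means and does not depend on the mixed model's covariance. Separately, the Protocol copy of the table shows 0.66 at d = 0.6 and 0.58 at d = 0.7, which do not reproduce.

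**What the random intercept implies.** Let s₁ and s₂ be the true residual SDs at the two visits, c their covariance (taken as non-negative) and r = s₂/s₁. With complete data the fitted common variance is the average, (s₁² + s₂²)/2. Therefore

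- model SE / true SE at the first follow-up: k₁ = √((1 + r²)/2)
- model SE / true SE at 6 months: k₂ = k₁/r
- large-sample type I error at each visit: 2 × {1 − Φ(1.96 × k)}

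Worked case, r = 1.2: (1 + 1.44)/2 = 1.22, so k₁ = √1.22 = 1.105 and k₂ = 1.105/1.2 = 0.920. Type I error is 3.0% and 7.1%.

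| SD ratio r (assumed) | k₁ | k₂ | Type I, first follow-up | Type I, 6 months |
|---|---|---|---|---|
| 0.67 | 0.85 | 1.27 | 9.5% | 1.3% |
| 0.8 | 0.91 | 1.13 | 7.6% | 2.7% |
| 1.0 | 1.00 | 1.00 | 5.0% | 5.0% |
| 1.1 | 1.05 | 0.96 | 3.9% | 6.1% |
| 1.2 | 1.10 | 0.92 | 3.0% | 7.1% |
| 1.3 | 1.16 | 0.89 | 2.3% | 8.0% |
| 1.5 | 1.27 | 0.85 | 1.3% | 9.6% |

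For r = 1.3: (1 + 1.69)/2 = 1.345, k₁ = 1.160, k₂ = 1.160/1.3 = 0.892.

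**Why the interaction test is safe.** The model variance of the difference between visits is 2 × {(s₁² + s₂²)/2 − c} = s₁² + s₂² − 2c, which is the true variance. With complete data the group-by-time test therefore keeps its size.

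**Check by simulation.** The planned fixed effects were fitted by REML to 2,000 data sets per scenario under no effect, with correlation 0.6 (assumed) and a t reference with n − 3 df. Monte Carlo error is about 1 percentage point (1.96 × √(0.05 × 0.95/2000) = 0.0096). Entries are type I error, first follow-up/6 months.

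| Scenario | Random intercept | Unstructured |
|---|---|---|
| 27 per group, complete, r = 1 | 4.5% / 4.4% | 4.9% / 4.4% |
| 27 per group, complete, r = 1.25 | 2.1% / 6.6% | 4.5% / 4.5% |
| 27 per group, complete, r = 1.5 | 0.7% / 8.4% | 4.2% / 4.3% |
| 30 per group, 20% random loss at 6 months (assumed), r = 1.5 | 1.4% / 10.8% | 5.6% / 5.3% |

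The interaction test in the complete-data runs at r = 1.25 and 1.5 had size 5.2% to 5.3% under both models.

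**The case against.** **The text says random effects, not random intercept.** This stands in part. A model with visit-specific residual variances would escape the criticism, and the plan does not exclude one, but neither document names it. A random slope is not a workable reading either: intercept variance, slope variance, their covariance and a residual variance make four parameters for three identifiable moments. The random intercept is the natural reading, but it is an inference.

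**The size depends on an SD ratio that the documents do not give.** This stands. At 1.1 the standard errors are off by only about 5%, at 1.0 there is no error, and below 1 the direction reverses. A reader might infer that the 0.05 level fails at both visits in any case. It fails only if the variances differ.

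**A reader might also infer that the visit-specific SDs are lost to the next trial.** On that view a 6-month-based design at a ratio of 1.5 would be undersized by 28% (pooled over true variance = 1.625/2.25 = 0.72). The documents do not support this. Both already plan descriptive means and SDs for the follow-up measures, so a change in spread would be visible. The shortfall needs a planner to set those SDs aside in favour of the pooled model variance, and nothing says that will happen. What the plan says will feed the next sample size are the contrast estimates, which stay unbiased with complete data, and the correlations between follow-ups.

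**This is a pilot with no multiplicity adjustment and no decision rule tied to these p-values.** This stands, and it limits the consequence. It does not make the per-visit confidence intervals correct.

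**A log transform might even out the spread.** Possibly, but only if non-normality triggers it.

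**Conclusion.** The point holds as a conditional, low-cost improvement. It rests on two assumptions: that the patient random effect means an intercept with one residual variance, and that the residual SDs differ between follow-ups. If both hold, the per-visit standard errors and intervals are wrong in opposite directions. For 6-month SDs 1.1 to 1.5 times those at the first follow-up, large-sample type I error runs from about 4% down to 1% at the first follow-up and from about 6% up to 10% at 6 months. The pattern is mirrored for ratios below 1. With complete data the effect estimates and the group-by-time test are not affected, and the power table does not change. The point does not show that the pilot would mislead the sizing of the next trial.

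**What to change.** In Protocol section 9.4 and the matching SAP paragraph, replace the patient random effect with an unstructured 2x2 within-patient covariance. Keep baseline as a covariate, fit by REML and use Kenward-Roger degrees of freedom. Apply this to both co-primary outcomes and to the secondary outcomes that reuse the model. Take the visit-specific residual SDs and their correlation from that model for planning, alongside the descriptive SDs already promised; the residual SDs are adjusted for baseline and the descriptive ones are not.

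The cost is one more covariance parameter (three instead of two) and a one-line change in code. Design, sample size and data collection are unchanged. At equal variances the simulation shows no visible loss with 27 per group.
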